INTERVENTIONAL RESEARCH PROTOCOL

STUDY INFORMATION

- **Title of Project:** *Healthy ME: Advancing Health Equity in Lymphatic Pain and Lymphedema in Black and Hispanic Women with Breast Cancer*
- **Principal Investigator Name:** [name] [name], RN, FAAN
- **Principal Investigator Department:** University of Missouri-Kansas City School of Nursing and Health Studies
- **Principal Investigator Contact Info:**
[contact]
Email: [contact]
- **Protocol Version and Date:**
V1-10 12 2023

ABSTRACT

PURPOSE/SPECIFIC AIMS The purpose of this project is to adapt The-Optimal-Lymph-Flow (TOLF) behavioral intervention to be culturally appropriate, and subsequently test the intervention in Black and Hispanic patients. Our team has developed and tested behavioral intervention program TOLF that builds patients' self-management skills to promote lymph flow and results in complete pain reduction, reduced lymph fluid level, reversed mild lymphedema, and improved quality of life (QOL). Of concern, this promising intervention has not been adapted to reduce patient barriers (e.g., relevance, cost, time, travel, competing demands) and system barriers (e.g., intervention availability, staffing, therapist) to timely interventions faced by Black and Hispanic women. Specific aims are to:

Aim 1: Engage Black and Hispanic women (N=24) in adapting TOLF to be highly culturally appropriate. We will conduct focus groups to refine TOLF focusing on barriers faced by and preferences of Black and Hispanic women.

Aim 2: Conduct a pilot randomized controlled trial (RCT) (N=60) equally allocating women to either 1) TOLF or 2) lymphedema education (e-Lymph) to examine feasibility, acceptability, and examine primary outcomes (lymphatic pain, pain severity and interference, and lymph fluid level) and secondary outcomes (daily living function, psychological distress, QOL, self-efficacy for pain management) of the culturally appropriate behavioral interventions.

RATIONALE/SIGNIFICANCE OF THE STUDY. Lymphatic pain refers to pain, aching or soreness in the ipsilateral body or upper limb following breast cancer treatment. More than half of the 3.8 million women with breast cancer suffer lymphatic pain which leads to impaired daily living function, psychological distress, and compromised QOL. Most importantly, lymphatic pain is significantly associated with lymphedema, a chronic and incurable condition caused by an abnormal accumulation of lymph fluid. Black and Hispanic women are three times as likely to suffer from lymphedema compared to White women. Timely intervention for lymphatic pain can decrease the risk and severity of lymphedema. However, there are persistent barriers to timely interventions faced by Black and Hispanic women with breast cancer – a group at high risk for developing lymphedema, pain, and other negative breast cancer related outcomes.

THEORETICAL FRAMEWORK. Self-efficacy theory guides the project. Behavioral pain interventions focus on training patients on self-management skills to be implemented in their daily lives.

MAIN RESEARCH VARIABLES. Behavioral pain intervention (IV), Outcomes (DVs): lymphatic pain, pain severity and interference, lymph fluid level, daily living function, psychological distress, QOL, self-efficacy for pain management.

DESIGN. Qualitative and randomized clinical trial (RCT)

SETTING. All participants will be recruited from UMKC University Health and surrounding communities.

SAMPLES. Black and Hispanic women with lymphatic pain

METHODS. Focus groups will be conducted with Black and Hispanic women to gather data that will lead to culturally appropriate adaptation of TOLF. Then, a pilot RCT will be used to examine feasibility, acceptability, and evidence of future efficacy of this culturally adapted intervention.

IMPLICATIONS FOR PRACTICE. The successful completion of the project will advance health equity in pain and lymphedema by making this culturally appropriate, highly accessible, and effective behavioral intervention available to Black and Hispanic women.

1.0 Research Design

1.1 Purpose/Specific Aims

Lymphatic pain affects more than half of 3.8 million women treated for breast cancer in the United States.¹⁻⁴ Lymphatic pain significantly compromises patients' daily living function,² increases psychological distress,⁵ and decreases quality of life (QOL).⁶⁻⁷ Lymphatic pain refers to various pain (e.g., aching or soreness) in the ipsilateral body or upper limb due to a compromised lymphatic system from breast cancer treatment.²⁻⁴ Lymphatic pain is significantly associated with lymphedema,²⁻⁵ a chronic and incurable condition caused by an abnormal accumulation of lymph fluid in the ipsilateral body or upper limb.⁸ **Black and Hispanic women are three times more as likely to suffer from lymphedema compared to White women following breast cancer treatment.**⁹⁻¹⁰ High rates of lymphedema and lymphatic pain in Black and Hispanic women are partially due to health inequities as these groups are more likely to be diagnosed with advanced stages of cancer leading to more aggressive treatments.¹¹⁻¹² Effective management of lymphatic pain can decrease the risk of developing lymphedema and lessen lymphedema severity.¹³⁻¹⁸ However, there are persistent barriers to timely interventions faced by Black and Hispanic patients – a group at high risk for developing lymphedema, pain, and other negative cancer related outcomes.⁹⁻¹² Ethnic disparities in offering interventions after pain complaints and financial hardship are identified barriers.^{2,9-12} The proposed work aims to decrease health inequities in lymphatic pain intervention in Black and Hispanic women with breast cancer and ultimately decrease the development of and lessen the severity of lymphedema, a chronic and debilitating illness for these women.

We have developed and tested in largely White patients a non-pharmacological, behavioral intervention, The-Optimal-Lymph-Flow (TOLF) that builds patients' self-management skills to promote lymph flow and results in complete pain reduction, reduced lymph fluid level, reversed mild lymphedema, and improved QOL.¹³⁻²¹ Of concern, this promising intervention has not been adapted to reduce patient barriers (e.g., relevance, cost, time, travel, competing demands) and system barriers (e.g., intervention availability, staffing, therapist) to timely interventions faced by Black and Hispanic women. The purpose of this two-phase project is to adapt The-Optimal-Lymph-Flow (TOLF) a non-pharmacological, behavioral intervention to be culturally appropriate, and subsequently test the intervention in Black and Hispanic patients. We will recruit study participants from UMKC University Health. Women of minority are more likely to have comorbid health problems (e.g., obesity/high body mass index [BMI]) and financial hardship,^{2,11-12,25-28} which are risk factors for lymphatic pain and lymphedema.^{2-3,30-32} Based on prior research and our preliminary studies,³⁻¹⁸ our **central hypothesis** is that lymphatic pain increases the risk of lymphedema and behavioral intervention can reduce pain and lymph fluid level to prevent lymphedema. Our group is **uniquely qualified** to lead this project due to our expertise in lymphedema, lymphatic pain, health disparity, breast cancer, pain and cancer-related symptoms, and the clinical volume of Black and Hispanic patients with breast cancer at our center. Guided by self-efficacy theory,³³⁻³⁴ the specific aims of this two-phase project are to:

Aim 1: Engage Black and Hispanic women (N=24) in adapting TOLF to be highly culturally appropriate. We will conduct focus groups to refine TOLF focusing on barriers faced by and preferences of Black and Hispanic women.

Aim 2: Conduct a pilot randomized controlled trial (RCT) (N=60) equally allocating women to either 1) TOLF or 2) lymphedema education (e-Lymph) to examine feasibility, acceptability, and examine primary outcomes (lymphatic pain, pain severity and interference, and lymph fluid level) and secondary outcomes (daily living function, psychological distress, QOL, self-efficacy for pain management) of the culturally appropriate behavioral interventions.

Impact. Our project has the potential to have a major impact on reducing cancer-related disparities (lymphedema, pain, QOL) among Black and Hispanic women. The project will also build clinical capacity to provide quality care for lymphatic pain and lymphedema prevention for women living in environmental justice communities. By focusing ethnic disparities in offering behavioral interventions to Black and Hispanic

[figure not shown]
women, adapting and testing interventions for culturally sensitive care, this project addresses ONS Research Agenda Priority of Cancer Health Disparities and Promote Equity in Oncology Healthcare Access.

1.2 Research Significance

Lymphatic pain is a cardinal sign for an early stage of lymphedema.³⁵⁻³⁷ Patients who report lymphatic pain are nearly twice as likely to develop lymphedema.⁴ Without timely intervention in this early stage, lymphedema can progress into a chronic condition that no surgical or medical interventions can cure.⁸ In addition, lymphatic pain and lymphedema significantly impact patients' daily living function,^{2,38-39} psychological distress,⁵ and QOL.⁴⁰⁻⁴¹ The burden from lymphatic pain and lymphedema and can be even higher for Black and Hispanic women. Studies show that women of racial minority background experience delays in breast cancer treatment and/or inadequate treatment.^{10-12;42-45} Later stage diagnosis and delayed treatment lead to high risk of lymphedema and pain due to the needs to have more aggressive surgical treatment, more lymph nodes removed, and radiation.⁹⁻¹² Further, women of minority are more likely to have comorbid health problems (e.g., obesity),^{2,11-12;25-28} the risk factor for lymphatic pain and lymphedema.^{3;31-34} Women with financial hardship are 4.64 times more likely to report lymphatic pain.² Our recently published study detailed that patients with lymphatic pain reported impairments in 45% of ADLs and had a significantly increased risk of having difficulty in performing all the 13 ADLs (i.e., cooking, using a knife, writing/typing, cleaning, vacuuming, laundry, carrying objects, yard work, dressing self, bathing self, driving, making bed, and taking care of children).² Patients' psychological distress was further compounded when they felt that clinicians did nothing but "pity me."⁵ Disparities among women with breast cancer in environmental justice communities are maintained by a lack of cost-effective, accessible, and appropriately adapted supportive care opportunities found at more resourced medical centers.⁴³⁻⁴⁴ This results in a large symptom burden (i.e., lymphatic pain,) for patients, providers, and healthcare systems.

1.3. Theoretical Framework

Self-efficacy theory guides the proposed project.³³⁻³⁴ Behavioral interventions for managing lymphatic pain and lymphedema prevention focus on building patients' self-management skills to be implemented in their daily lives outside clinical settings without professionally administered therapy (e.g., by therapists or nurses).¹⁴⁻¹⁷ To achieve the therapeutic effects, patients have to execute self-management skills outside of clinical settings. Self-efficacy is defined as a person's belief in his/her ability to perform specific skills to reduce lymphatic pain and to prevent lymphedema. (See Adjacent **Figure**).

1.4. Review of Literature

State-of-the-Art for Lymphatic Pain and Lymphedema Prevention. Behavioral strategies are commonly used for pain control in cancer patients.⁵⁰⁻⁵³ Pharmacologic interventions, such as NSAIDs, opioids, antiepileptics, ketamine and lidocaine, have very limited effects on pain;^{8,46-49} Very limited RCTs were designed to build patients' self-management skills to manage lymphatic pain, a major predictor for lymphedema, impaired daily living function, psychological distress, and poor QOL.²⁻⁵ Majority of RCTs were devoted to lymphedema treatment administered by professional therapists, such as Complete Decongestive Therapy (CDT), compression garments and bandaging, pneumatic pumps, or supervised physical therapy.⁵⁰⁻⁵² The cost and time to attend therapist-administered treatments, the potential harm by the poor fit of compression sleeve, and patients' unwillingness to wear and cost for compression sleeve remain wide-spread challenges for patients. These challenges can be even more impactful for Black and Hispanic patients who face personal barriers (e.g., time, travel, competing demands, cost) and system barriers (e.g., treatment availability, staffing, therapist).

Behavioral Interventions Are Efficacious in Treating Lymphatic Pain. Lymphatic pain is associated with increased lymph fluid accumulation,^{2,4} and inflammatory responses.³⁹⁻⁴¹ Limited research tested integrative behavioral interventions based on physiological (lymph fluid accumulation and inflammation) and cognitive principles (low self-efficacy). We have developed and extensively tested a non-pharmacological, behavioral *The-Optimal-Lymph-Flow* (TOLF) intervention that includes strategies to promote lymph flow: therapeutic lymphatic exercises, healthy diet (i.e., nutrition-balanced, portion-appropriate diet, adequate hydration), and proper sleep.¹³⁻²¹ The core TOLF intervention is 8-minute TOLF lymphatic exercises to promote lymph flow (i.e., muscle-tightening deep breathing, muscle-tightening pumping, and limb mobility exercises).¹³ TOLF includes a website that provides patients with TOLF intervention materials, information, and daily assessments used to personalize sessions.¹³⁻²¹ One dose of TOLF lymphatic exercises can produce immediate significant effects on reductions in pain, swelling, and reduction in lymph fluid levels.¹³ Our recent publish RCT demonstrated that 50% of patients who received TOLF intervention achieved a complete pain reduction (50% vs 22%; OR=3.56, CI = [1.39, 9.76], p=0.005) compared to control of 22%.¹⁴ Given TOLF is efficacious, focusing on self-management skills, having immediate therapeutic effects, and welcomed by patients (only 6% attrition), TOLF may provide particular benefits for Black and Hispanic patients who face personal challenges of time, travel, competing demands, cost for therapist-administered treatment. In addition, technologically-driven delivery model makes it easy for community-level implementation to address system barriers of intervention availability, staffing, therapist.

1.5. Innovation

This project is innovative for multiple reasons. **1)** This will be the first study to address ethnic disparities and system barriers (e.g., intervention availability, staffing, therapist) in offering behavioral interventions to Black and Hispanic women with lymphatic pain to prevent lymphedema by adapting efficacious, non-pharmacological, behavioral interventions to be culturally appropriate, and subsequently test the interventions in Black and Hispanic patients. **2)** The project is innovative in disrupting place-based health disparity and social determinants of health on lymphatic pain and lymphedema prevention. There is an increased urgency for completing the proposed project in the population of interest rather than hoping to recruit “enough” Black and Hispanic participants to examine disparities. Our ongoing community engagement, our geographic location, and our current and prior successful experiences²⁵⁻²⁶ with patients in environmental justice communities enable us to engage Black and Hispanic patients in these hard-to-reach settings. **3)** The use of technologically-driven intervention delivery not only enhances the fidelity and transparency of the interventions but also the reproducibility of the interventions, which may enhance the generalizability and dissemination of the interventions. **4)** This project is innovative in addressing major personal barriers (e.g., cost, time, travel, competing demands) faced by Black and Hispanic patients. For example, the adaption of the daily 8-minute TOLF lymphatic exercises, which is effective even with one dose¹³ and easy for patients to implement it,¹³⁻¹⁸ in turn, it addresses barriers of limited time and competing demands faced by Black and Hispanic women. **5)** Because previous research found that traditional measures of ADLs (i.e. toileting, ambulation, continence, and feeding) are less relevant to women with breast cancer,^{2,5,38-41} the breast cancer specific measures of ADLs is another innovation.^{2,38} **6)** The proposed intervention is cost-effective and sustainable (e.g., by intervening in the health system and reducing the reliance on pain medication and medical intervention). Thus, our project provides a unique opportunity to provide empirical evidence and generate knowledge to advance health equity in lymphatic pain and lymphedema prevention.

1.7. Research Design and Methods

Design. This two-phase project uses qualitative (i.e., focus group) and pilot randomized clinical trial (RCT) design to adapt TOLF to be culturally appropriate, and subsequently test the intervention in Black and Hispanic patients. (See Adjacent Figure for study design.)

Sample. The participants are Black and Hispanic women (over age 18) with lymphatic pain following breast cancer treatment. These women will be recruited for the **Phase I focus groups** (N=24), and the **Phase II RCT** (N=60). Participants will include

women who **1)** have received surgical treatment for breast cancer at least 3 months prior to the study enrollment, **2)** report persistent or intermittent pain/aching/soreness in the ipsilateral body or upper limb; **3)** self-identify as either Black or Hispanic; and **4)** are able to understand the study protocols presented in English. Exclusion criteria include: **1)** presence of a serious psychiatric condition (e.g., schizophrenia, suicidal intent) indicated by medical chart, treating oncologist or other staff, or study staff interactions that would contraindicate safe study participation; **2)** known metastatic disease (Stage IV), recurrence of cancer, or lymphedema due to cancer recurrence, or other bulk disease in the thoracic or cervical regions; **3)** were diagnosed or treated for lymphedema.

Setting. All participants in the proposed work will be recruited from UMKC (University of Missouri-Kansas City) Health System and Kansas City Metropolitan eastside communities, which is recognized as the fifth most economically and racially segregated city in the U.S. Black and Latino individuals in Kansas City, Missouri (KCMO) die up to 18 years earlier than White individuals. Majority of breast cancer patients are Black and Hispanic and rely on Medicaid and Medicare for health insurance. Drs. [name], [name] have strong collaboration with University Health and will be responsible for the recruitment.

Recruitment. Our team consists of experienced clinical trials investigators with extensive histories of successful recruitment. We will use electronic medical records (EMR), tumor registry information, and clinic staff to identify potential trial participants. The clinical research coordinator will send an email to the treating oncologist to alert them of potential participants. Participating oncologists will alert the study team if there is a known psychotic disorder, suicidal intent, or other conditions that would contraindicate safe study. Potential participants will be mailed a letter or an email or a phone call from their provider or the research study team with study information. The communication will let the patient know that a member of the study team will call them to follow-up; an opt-out phone number will also be provided. Following recruitment communication, study staff will contact potential participants to assess interest in the study and to conduct pre-screening. If patients meet eligibility criteria, they will be invited to schedule informed consent in-person or via telephone. All participants will continue to receive routine standard medical care from their medical team. The study team will closely track participant recruitment; additional clinics will be quickly implemented if recruitment has not been met at 90% in any 3-month period.

Phase I Focus Groups. The TOLF intervention will be adapted to be culturally-appropriate using input from Black and Hispanic women with lymphatic pain (N=24; 2 groups: Black [n=12] and Hispanic [n=12]). To our

knowledge, this is the first study to systematically adapt efficacious behavioral interventions for Black and Hispanic women with lymphatic pain. To adapt the interventions, we will use qualitative data gathered during focus groups held separately with Black and Hispanic patients. Semi-structured interview guides will be used to facilitate focus groups; we have drafted a focus group discussion guide. The group leaders (Drs. [name], [name], and [name], co-investigators) will guide the discussion. The interview guides will be reiterated following each group to attend to themes of previous groups. The aim of the focus groups is to better understand the needs and preferences of the Black and Hispanic women with lymphatic pain. Each Black and Hispanic woman will participate in two sessions of focus group. In Session I, Black and Hispanic women will be systematically presented with the content of TOLF and be asked to provide their opinions on the content, the current patient handouts, and how to modify the handouts, the intervention format (e.g., in-person, web-based, telehealth conferencing, timing of interventions, length of the intervention). Participants will be asked to practice TOLF self-management skills for a week before Session II. Session II will focus on barriers in implementing TOLF self-management skill to further refine the interventions. All focus groups will be 60 minutes long and audio recorded. Our team has extensive experience conducting qualitative interviews and focus groups, as well as a using focus groups to inform intervention adaptation and development.^{5,25-26,53,58}

Intervention/Independent Variables.

Phase II RCT Randomization and Conditions.

In Phase II RCT, a total of 60 participants will be recruited consisting of 30 Black and 30 Hispanic patient participants, respectively. Following baseline assessment, 30 Black and 30 Hispanic patient participants will be randomly assigned with equal allocation to one of two conditions: 1) TOLF (Intervention), or 2) e-Lymph (Control). e-Lymph includes training sessions on the lymphatic system, lymphedema, lymphedema diagnosis and measurement, risk of lymphedema. The major goals of skill training sessions for TOLF and e-Lymph are described in **Table 1**. Randomization will be blocked by ethnicity to ensure reasonable balance in each treatment condition. The data manager on this study who is not involved with recruitment will randomly draw a number of 1, or 2 to be given the participant's study number (not name) to randomize the participant. Our research evaluator will not

Patient Sessions	The-Optimal-Lymph-Flow (TOLF)	Lymphedema Education (e-Lymph)
1 In-person (40 minutes)	
 In-person learning the Importance of promoting lymph flow In-person training and practicing lymphatic exercises using Kinect-TOLF Learning on lymphatic system, lymphedema, lymphedema diagnosis and measurements Home practice planning 	
 In-person learning on lymphatic system, lymphedema, lymphedema diagnosis and measurements
2 Virtual (20 minutes)	
 Home practice review Learning the importance of large muscle exercises to promote lymph flow Home practice planning for large muscle exercises (e.g., walking, running, dancing, yoga) 3 times per week for 30 minutes Home practice planning 	
 Home review Questions and Answers
3 Virtual (20 minutes)	
 Home practice review Learning the importance of weight for lymph flow Planning for healthy diet and sleep hygiene Home practice planning 	
 Home review Questions and Answers
4 Virtual (20 minutes)	
 Home practice review Planning for maintenance of all learned skills 	
 Home review Questions and Answers
Program Materials	TOLF materials include information about the lymphatic system, lymphedema, lymphedema diagnosis and measurement, risk of lymphedema, healthy diet, sleep hygiene, and daily therapeutic lymphatic exercises training and videos; participants will be granted access to all of the materials in TOLF website. A workbook with worksheets and pencil will be given to participants for recording.	e-Lymph materials include information about the lymphatic system, lymphedema, lymphedema diagnosis and measurement, risk of lymphedema; participants will be granted access to the e-Lymph materials on TOLF website.

be involved in recruitment or have other contact with participants; she/he will be blinded to participant randomization and conduct all study procedures where blinding is indicated (e.g., assessments). All efforts will be made for study staff and oncologists to be blinded to participant condition.

The-Optimal-Lymph-Flow (TOLF).

TOLF includes training sessions on the lymphatic system, lymphedema, lymphedema diagnosis and measurement, risk of lymphedema, healthy diet, sleep hygiene, and daily lymphatic exercises. It has 8 avatar videos with step-by-step instructions for TOLF lymphatic exercises to promote lymph flow. In Phase I, Aim 1 will adapt the intervention to be culturally sensitive, some changes are expected in the final intervention protocol. It is expected that participants will complete initial in-person or telehealth virtual 40-minute session, and 3 virtual telehealth sessions with each session for 20-minute over the course of 8 weeks. In initial in-person session, the participant will be trained to

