Statistical Analysis for Phase II/Aim 2. Sixty patients (N=60) will be randomized into two equal sized groups with 1:1 ratio, either to TOLF or e-Lymph group. *Feasibility* will be assessed by examining (a) study accrual of breast cancer patients (N=60 over 9 months), (b) protocol adherence (>80% adherence to the protocol [defined in this study as the degree to which participants are willing and able to complete the intervention exposure], e.g., TOLF or e-Lymph), and (c) participant retention (>80% data collected at the study appointments). *Acceptability* will be assessed post-intervention using the validated scale of patient satisfaction and acceptability and exit interview.⁷⁷ *Evidence of Promising Outcomes.* Assuming a minimum protocol adherence of 80%, there will be at least 48 participants who will rate whether treatment is acceptable. Assuming acceptability is 50% which has the most conservative precision interval, the acceptability will be estimated within 8%.

Primary Endpoint. The primary endpoint is the complete reduction of lymphatic pain and reduced pain severity and interference reported by participants, and reduced lymph fluid level at week 13 post intervention.

Statistical Analysis for Outcomes. We hypothesize that participants who receive the TOLF will have better primary and secondary outcomes than participants who receive the control e-Lymph over time. Since outcomes will be measured at week 0 (baseline), 9 weeks and 13 weeks post intervention, generalized estimating equation (GEE) model will be used for analyzing each outcome to accommodate the correlation among the repeated measurements within a same subject.⁷⁸ Different working correlation matrices will be tested to select the most appropriate one for the GEE models. Identity link and logit link will be used for continuous outcomes (lymphatic pain severity, pain severity and interference, lymph fluid level, daily living

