function, psychological distress, QOL, and self-efficacy for pain management) and binary outcome (complete pain reduction), respectively. The predictors include two indicators of intervention and control groups respectively. Covariates found to be significantly different between the groups at baseline, will be included in the GEE model.⁷⁹ If the primary outcomes of the intervention group are significant at alpha 0.05, we will conclude the intervention works better than the control. Proper methods will be used to address any missing data to maximize the statistical power of our analyses and reduces the likelihood of systematic bias in estimates.

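### The draw of 1 or 2 contains no step that carries out the stated blocking by ethnicity or secures two equal groups, and ethnicity is not committed to the GEE model

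*Combined protocol and SAP*

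**What the plan says.** Section 1.7 (Phase II RCT Randomization and Conditions) sets the sample: "a total of 60 participants will be recruited consisting of 30 Black and 30 Hispanic patient participants". These women "will be randomly assigned with equal allocation to one of two conditions". It then states a restriction: "Randomization will be blocked by ethnicity to ensure reasonable balance in each treatment condition". The next sentence gives the mechanism: the data manager, who has no part in recruitment, "will randomly draw a number of 1, or 2" for each study number. Section 1.9.b (Statistical Analysis for Phase II/Aim 2) is firmer about the result: the sixty patients "will be randomized into two equal sized groups with 1:1 ratio".

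The text gives no block size, no list prepared in advance, no separate sequence for each ethnic group, and no rule on whether draws are independent or without replacement.

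On analysis, section 1.9.b names only the group indicators as predictors in the GEE models. Other covariates enter only if they differ significantly between the groups at baseline. Section 1.8 lists race and ethnicity among the data collected under potential covariates, but nothing commits either to the model.

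**The concern.** The aim (blocked by ethnicity, two equal groups) and the instruction (draw a 1 or a 2 for each woman) do not visibly connect. A data manager who follows the instruction literally makes 60 independent two-way draws, and nothing in that process returns the counts to balance overall or within Black or Hispanic women. Ethnicity is the one factor the design sets out to balance, and at 60 women a chance imbalance can be large enough to complicate the comparison.

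The analysis rule adds to this. If blocking works, ethnicity will not differ significantly between arms, so the rule leaves the blocking factor out of the model. If blocking is not carried out, a moderate imbalance will often fall short of significance, and the rule leaves it out again.

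**Working it through.** **Inputs.** N = 60, made up of 30 Black and 30 Hispanic women (section 1.7); two groups of equal size, hence 60/2 = 30 per arm (section 1.9.b); a draw of 1 or 2 per study number (section 1.7). The plan gives no sample-size or power derivation, so 30 + 30 is a design statement, and it is tested here against two readings of the draw.

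**Reading A: independent draws, probability 1/2 each.**

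1. Exactly 30/30: C(60,30)/2^60 = 0.103.
2. Arms of 26/34 or more unequal: 2 × P(Bin(60, 0.5) ≥ 34) = 0.366.
3. Ethnic imbalance within an arm. Let B and H be the numbers of Black and Hispanic women in one arm, each Bin(30, 0.5). Then B + (30 − H) is Bin(60, 0.5), and B − H is that variable minus 30. So P(|B − H| ≥ 6) = 2 × P(Bin(60, 0.5) ≥ 36) = 0.155. Both arms have the same absolute difference, because (30 − B) − (30 − H) = −(B − H).

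**Would the baseline-significance rule catch it?** Take 18 Black and 12 Hispanic women in one arm and 12 and 18 in the other. The chi-square without continuity correction is 60 × (18×18 − 12×12)² / 30⁴ = 60 × 180² / 810,000 = 2.4, p = 0.12; Fisher's exact p = 0.20. No adjustment follows, although the share of Black women differs by 60% − 40% = 20 percentage points. Summing over all splits under Reading A, a difference of 6 or more that is also non-significant by this chi-square has probability 0.103. That is about two thirds of the 0.155.

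**Power cost of unequal arms.** For illustration only, take the complete-pain-reduction rates that section 1.4 reports for the earlier TOLF trial, 50% v 22%, and the alpha of 0.05 in section 1.9.b, assumed two-sided. The plan does not call these rates design assumptions. Power = Φ[(|p1 − p2| − 1.96·SE0)/SE1], with SE0 pooled and SE1 unpooled. At 30/30, the pooled rate is 0.36, SE0 = √(0.36 × 0.64 × 2/30) = 0.1239 and SE1 = √((0.25 + 0.1716)/30) = 0.1185, so power = Φ(0.313) = 62.3%.

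| TOLF / e-Lymph | Power |
|---|---|
| 30 / 30 | 62.3% |
| 24 / 36 | 61.7% |
| 36 / 24 | 59.4% |
| 22 / 38 | 60.8% |
| 38 / 22 | 57.6% |

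The loss is 0.6 to 4.7 points. On the variance scale, 26/34 costs (1/26 + 1/34)/(2/30) = 1.018, under 2%.

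**Reading B: draws without replacement within blocks, separately for each ethnic group of 30.** Block sizes that divide 30 (2, 6, 10 or 30) finish at exactly 15/15 per group and 30/30 overall. Blocks of 4 leave 30 − 7×4 = 2 places in a part block, so the final difference is at most 2 per ethnic group and at most 4 overall. This reading delivers the stated design, exactly or very nearly.

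**The case against.** The strongest reply is that the sentence just before the draw states the blocking. Read together, the two sentences fit slips marked 1 and 2 drawn without replacement within ethnicity blocks, and nothing says the draws are independent. This stands. A reader might infer that the draw simply is simple randomisation, but the documents do not support that. They leave the point open, and the figures under Reading A are conditional on it.

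The plan also promises only reasonable balance by ethnicity, and equal allocation can mean a 1:1 probability, which a fair draw satisfies. This stands too: 15/15 in each ethnic group is not a stated promise, and a miss on that target should not be counted against the plan. The statement of two equal-sized groups in section 1.9.b is stricter, and a 1:1 probability alone does not secure it.

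A reader might also take a lopsided split inside one ethnic group as evidence that treatment is confounded with ethnicity. It is not: if both groups split 12/18 in the same direction, each arm still holds equal numbers of Black and Hispanic women. The relevant event is the difference between the two splits, hence the 15.5%.

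Finally, this is a pilot with feasibility and acceptability among its aims, chance imbalance under fair randomisation is not systematic bias, and the power loss is minor. All of that is right, and it limits the seriousness of the point. It does not supply the missing procedure.

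**Conclusion.** The point holds as a gap between the stated design and the written mechanism, with moderate confidence. As described, the allocation cannot be reproduced or audited, and the reader must supply the step that makes it blocked. If draws are not restricted within ethnicity blocks, exactly 30/30 has probability about 10%, and Black and Hispanic counts in an arm differ by 6 or more with probability about 15.5%. Both figures assume independent fair draws and full recruitment of 30 + 30. If draws are restricted within blocks, the design is delivered and only the wording is deficient.

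The consequence is moderate: little power is at stake, and the main loss is the balance by ethnicity. Separately, and on either reading of the draw, the blocking factor is not committed to the GEE models, and the significance rule is not a dependable substitute.

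The text between sections 1.5 and 1.7 was not available for this review. If it specifies the allocation sequence, the first part of the point falls away.

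**What to change.** 1. In section 1.7, replace the draw with a 1:1 permuted-block list generated before enrolment, stratified by Black/Hispanic and held by the data manager. Keep block sizes from recruiting staff. With blocks of 2 and 4, the final imbalance is at most 2 per stratum. If exact equality is wanted, let the block sizes in each stratum sum to 30 (for example seven blocks of 4 and one of 2: 28 + 2). Release of each assignment after the baseline assessment is already in the plan and should stay.
2. In section 1.9.b, include ethnicity as a fixed covariate in every GEE model, whatever its baseline p-value, and bring the wording on group sizes into line with the list.

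The cost is a few sentences of protocol text, a list that takes minutes to generate, and one extra model parameter. No added patients, staff or visits are needed. For the binary outcome with the logit link, the reported odds ratio is then conditional on ethnicity, and the text should say so.
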